Power assessment proceeded as follows, using a Monte Carlo approach.²⁵ We used available data to define a baseline period of 1/1/2019-12/31/2019. In a bootstrap procedure, individuals were selected with replacement from within each hospital, once to represent baseline data and separately to represent “intervention period” data. Hospitals were then “randomized” to intervention or control according to multiple parameters, including number of admissions with abdominal infection and ES-DOT. We then modified the outcomes for the bootstrapped individuals in the “intervention” period in the “intervention” arm to reflect the effect of the intervention.²⁹

We assessed power to identify an overall 12.5% relative reduction in ES-DOT. This effect was implemented by reducing the relative empiric days of therapy for each admission which was exposed to the CPOE prompt. The amount of reduction was a uniform random variate between 0.75 and 1. For example, if the bootstrapped patient initially received 8 ES-DOT and was assigned to have a 12.5% reduction, then that admission intervention ES-DOT would be reduced to 7 days ($8*0.875=7$). The reduction of ES-DOT was selected with a lower bound determined by the investigators as the minimal effect achieved that would be clinically meaningful. Using this method, we have $\geq 99.9\%$ (99.6-99.9%) power to detect this effect.

Since adoption of the intervention will be heavily influenced by the ability to demonstrate safety, our study size was based on the power to detect non-inferiority for safety outcomes. We used methods similar to the above to calculate the power to identify at least a one day increase in length-of-stay for 12.5% of patients who had hospitalizations less than 14 days and found the power was 91.5% (CI 89.6-93.2%), where non-inferiority is defined as a hazard ratio no smaller than 0.98. For days to ICU transfer, we estimated the power to detect a 2% increase in transfers to the ICU on hospital day 3 through 14 to be $>99.9\%$ (CI 99.6-99.9%), where non-inferiority is defined as having a hazard ratio no greater than 1.1 (fewer days to ICU results in a hazard ratio above 1).

For completeness, we note that there are other pre-specified outcomes intended for exploratory analysis in secondary papers for the INSPIRE ABD trial in Table 4 below.

Table 4: Secondary Manuscripts - Other Pre-Specified Outcomes

Secondary Manuscripts (other pre-specified secondary exploratory analyses for later manuscripts)	

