The trial will be assessed among the cohort of adult admissions who: 1) have administrative claims codes indicating an abdominal infection is present on admission; 2) received any antibiotic within 3 days of admission; and 3) were admitted to a non-ICU location.

The rationale for including only the first three days of the admission is that this is when the actual status of the patient with respect to the need for an ES antibiotic is unknown. Bearing this in mind, antibiotics given during an associated emergency department visit on the date of hospital admission are counted toward the ES-DOT of the first hospital day.

The trial baseline period includes January 1, 2019 – December 31, 2019 (12 months). The intervention period includes January 1, 2023 – December 31, 2023 (12 months). The baseline was selected to include time prior to the arrival of the COVID-19 pandemic since hospital operations and case mix were dramatically affected between Winter 2020-Spring, 2022.¹⁻⁴ Although COVID-19 surges have continued to occur, clinical operations and patient case mix at most hospitals have largely returned to near pre-pandemic activity. We considered that a state of pre-pandemic normalcy returned by summer of 2022, and introduced our intervention on August 2, 2022. The period between then and December 31, 2022 is considered a phase-in period and is not used in trial evaluation.

Primary Statistical Analysis

The primary trial outcome is defined as the summed number of different ES antibiotics received during each empiric day, on the patient-admission level. An empiric day is a day within the first three days of an admission. We define this outcome as the Total Empiric Extended-Spectrum Days of Therapy (ES-DOT). For clarity, the calculation is as follows: we define a DOT for a particular ES antibiotic as a day in which any number of doses of that antibiotic is given. Different ES antibiotics are summed within each empiric day for each patient admission to determine DOT in that at-risk day.

The main trial results will be based upon as-randomized, unadjusted analyses of admission-level ES-DOT. We note that the national DOT measure defined by CDC is measured at the hospital level. We define ES-DOT at the individual admission level so that we can perform analyses on individuals.

The main evaluation of all outcomes will be based on the difference in differences between the intervention and baseline periods and between study arms.

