The unit of analysis will be individual admissions. Individual patients can contribute more than one admission. The analytic model will be a generalized linear mixed effects model for differences in differences, with random effects to account for correlation within hospital between period, within hospital within period between patient, and within patient between admission. We plan to use a Poisson model for analysis of outcomes as follows:

$$\log(y_{ijph}) = \beta_0 + \beta_1 A_{ijph} + \beta_2 T_{ijph} + \beta_3 A_{ijph} T_{ijph} + b_{0h} + b_{1h} T_{ijph} + g_j + \log(ed_j)$$

where y_{ijph} is the ES-DOT for patient i for admission j in period p at hospital h , and $A_{ijph} = 1$ if hospital h is in the intervention arm and 0 if not, and $T_{ijph} = 1$ if p is the intervention period and 0 if baseline period. The random effects b_{0h} and b_{1h} allow for different baseline mean admission-level ES-DOT for each hospital and each hospital in the intervention period, respectively. Equivalently, they allow for correlation within hospital at different levels at baseline and at follow-up. The random effect g_j allows each patient to have a different mean ES-DOT. Finally, ed_j is the number of empiric days in the admission. We note that it may not be possible to fit models with the g_j parameter, for various numerical and computational reasons—the most prominent being a relative sparsity of patients with readmissions. If that proves to be the case, we will randomly select one admission per patient and use the model above without that parameter and omitting the j subscript.

The assessment of trial success will be determined by assessing the significance of the arm by period interaction term β_3 , which estimates the log relative rate of the outcome due to being in the intervention arm in the intervention period. The exponentiated parameter estimate for β_3 is the estimated relative rate of ES-DOT per at-risk day due to the intervention, relative to the baseline period. For example, if β_3 had a negative value and a p-value <0.05 , we would conclude that the patient-specific CPOE smart prompts generated a benefit over routine care. Exponentiating the parameter value would provide an estimate of the relative reduction due to the intervention in the expected ES-DOT per at-risk day.

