The primary trial analysis will use an as-randomized unadjusted model with two-tailed significance set at alpha = 0.05. Secondary outcomes will be assessed using an as-randomized unadjusted model and will include adjustment for multiple comparisons with two-tailed significance set at alpha = 0.025 for the two secondary outcomes.

Subsequent analyses of the primary and secondary outcomes will include both as-treated and adjusted models. Adjusted models will account for individual characteristics such as age, gender, comorbidities, and prior history of MDROs as well as hospital characteristics such as hospital antibiotic resistance. We will also account for seasonality. All adjusters will be determined a priori. These analyses will be reported as point estimates with confidence intervals and without p-values. The reason for including these analyses is to provide additional

information related to the trial outcomes for readers to assess the effects of potential confounders. The reason to not include them in a formal multiple comparisons adjustment is because these analyses are non-independent evaluations relative to the as-randomized unadjusted analyses.

Safety Outcomes

Safety outcomes are required because a reduction in ES-DOT might be achieved only by incorrectly withholding ES antibiotics when they were necessary. Each safety outcome will be evaluated for non-inferiority using an as-randomized unadjusted analysis with a one-tailed significance set at alpha = 0.05. For length of stay, the non-inferiority margin is a hazard ratio of 0.98. For days to ICU transfer, the non-inferiority margin is a hazard ratio of 1.1 (fewer days to ICU results in a hazard ratio above 1). Analyses planned for these assessments are proportional hazards models with random effects for each time period, hospital, and admission. These models are sometimes called frailty or shared frailty models. Because these are safety outcomes, we do not intend to make adjustments for multiple comparisons in testing them, further increasing conservatism. As above, it may not be possible to include multiple admissions.

All analyses will be performed using current versions of SAS/STAT and/or R packages lme4 and coxme, unless better packages become available in the meantime.

Further Planned Analyses

We note that there are other pre-specified outcomes intended for exploratory analysis in secondary papers for the INSPIRE ABD trial in Table 5 below.

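### The difference-in-differences model estimates a baseline arm effect that randomisation sets to zero, which costs some precision, chiefly for the length-of-stay test

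*SAP*

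**What the plan says.** The SAP's Primary Statistical Analysis section specifies a Poisson "generalized linear mixed effects model for differences in differences". Its fixed effects are an intercept, arm (β1), period (β2) and arm by period (β3). Each hospital has a random intercept b0h and a random period effect b1h. On the decision rule: "The assessment of trial success will be determined by assessing the significance of the arm by period interaction term" β3. On scope: "The main evaluation of all outcomes will be based on the difference in differences between the intervention and baseline periods and between study arms".

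The baseline period is calendar 2019. Protocol E.1 places randomisation in the first quarter of the second study year, which the schedule in section F starts in June 2021. The Brief Overview gives 46 hospital units per arm.

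The SAP's Safety Outcomes section plans "proportional hazards models with random effects for each time period, hospital, and admission", tested with "one-tailed significance set at alpha = 0.05". It adds: "For length of stay, the non-inferiority margin is a hazard ratio of 0.98". The fixed effects of these Cox models are not written out. The protocol's sample-size section bases study size on the safety outcomes. It states power of at least 99.9% for the primary outcome and above 99.9% for ICU transfer. For length of stay it "found the power was 91.5% (CI 89.6-93.2%), where non-inferiority is defined as a hazard ratio no smaller than 0.98".

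Neither document mentions a baseline-constrained model or adjustment for baseline as a covariate. Protocol H.3 adds only a separate look at intervention-period effects by arm.

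**The concern.** Because the 2019 data were fixed before allocation, β1 is zero by design. Any difference between the arms in 2019 is chance. With arm, period and their interaction all free, the estimate of β3 is the plain change-score contrast: follow-up difference minus the whole baseline difference, a slope of 1 on baseline. Where baseline predicts follow-up with a slope below 1, part of what is subtracted is noise.

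Two alternatives use the same data. One omits β1 and lets the random-effects covariance set the weight given to baseline. The other regresses intervention-period outcomes on each unit's baseline value. Both handle chance imbalance, and neither fixes the slope at 1.

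The loss matters most where precision is scarce. That is length of stay, the only one of these tests with stated power clearly below 99.9%, and one with a margin of only 2% on the hazard scale.

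**Working it through.** **The plan's own figure.** The 91.5% comes from a bootstrap of hospital data that the documents do not contain, so it cannot be reproduced. Taking a true hazard ratio of 1:

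- Margin: −ln 0.98 = 0.0202. Power of 91.5% at one-sided 0.05 needs SE(log HR) = 0.0202/(1.645 + 1.372) ≈ 0.0067.
- Events per period: 0.93 × 99,000 = 92,070. The 93% is the stated share with a stay of 14 days or less. The 99,000 is the stated intervention-period size, assumed equal in 2019.
- One period, no clustering: SE = 2/√92,070 = 0.0066, power 92.2%. This is close to 91.5% but is not the planned model.
- Difference in differences with no hospital-by-period variance: SE = √2 × 0.0066 = 0.0093, power 69.9%. With 60,000 per period, the protocol's conflicting patient count, power is 51.7%.

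**Variance ratio.** Let V be the variance of a unit mean within a period (equal in both periods) and ρ the correlation of unit means between periods, with 46 units per arm.

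- Difference in differences: (2/46) × 2V(1 − ρ)
- Constrained baseline, or ANCOVA on baseline: (2/46) × V(1 − ρ²)
- Ratio: (1 − ρ²)/[2(1 − ρ)] = (1 + ρ)/2

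| ρ | Variance ratio | Reduction in SE | New power if 91.5% is the difference-in-differences power |
|---|---|---|---|
| 0.5 | 0.75 | 13% | 96.7% |
| 0.7 | 0.85 | 7.8% | 94.8% |
| 0.8 | 0.90 | 5.1% | 93.8% |
| 0.9 | 0.95 | 2.5% | 92.7% |
| 1 | 1.00 | 0% | 91.5% |

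In a simulation of 92 units the ratio was 0.76 at ρ = 0.5 and about 0.91 at ρ = 0.8, with type I error near 5% for both methods. Under pure random-walk drift (true slope 1, larger variance at follow-up) the two SEs were about equal.

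**Length of stay.** The documents give no hospital SDs, so those below are assumptions on the log-hazard scale. The sampling variance of a unit is 92/92,070 = 0.000999. Then V = stable² + period² + 0.000999, ρ = stable²/V, and power = Φ(0.0202/SE − 1.645).

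Example with stable SD 0.05 and hospital-period SD 0.03:

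- V = 0.0025 + 0.0009 + 0.000999 = 0.004399, and ρ = 0.568.
- Difference in differences: variance (4/46) × 0.004399 × 0.432 = 0.000165, SE 0.01285, power Φ(1.572 − 1.645) = 47%.
- Constrained: variance ratio 0.784, SE 0.01138, power Φ(1.775 − 1.645) = 55%.

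| Stable SD | Hospital-period SD | ρ | Difference in differences | Constrained | Gain (points) |
|---|---|---|---|---|---|
| 0.03 | 0 | 0.47 | 70% | 81% | 11 |
| 0.03 | 0.03 | 0.32 | 47% | 61% | 14 |
| 0.05 | 0 | 0.71 | 70% | 76% | 6 |
| 0.05 | 0.03 | 0.57 | 47% | 55% | 8 |
| 0.10 | 0 | 0.91 | 70% | 72% | 2 |
| 0.10 | 0.03 | 0.84 | 47% | 50% | 3 |
| 0.15 | 0 | 0.96 | 70% | 71% | 1 |
| 0.15 | 0.03 | 0.92 | 47% | 48% | 1 |

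The fall from 70% to 47% within each pair of rows comes from the assumed hospital-period variance, not from β1.

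**The case against.** The strongest reply is that this is a preference about efficiency. Difference in differences is unbiased and holds its error rate, and the primary and ICU tests have power to spare. That stands. A reader might infer that the planned test is invalid; nothing in the documents supports that.

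A second reply is timing. The protocol's analysis section dates itself to June 2022. The SAP is dated 29 March 2024, after the intervention period closed, and the protocol anticipated monthly data extracts. Replacing a pre-specified primary model at that stage could look data-driven. This also stands, and it determines how the fix is worded. The documents do not say whether outcomes by arm had been examined.

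Third, the allocation may have balanced the arms on baseline. The power simulation allocated hospitals using admissions and ES-DOT among other parameters, though length of stay is not named. Balance shrinks the difference being subtracted, but the model SE still charges for it. In a simulation pairing 92 units on baseline at ρ = 0.5, the difference-in-differences model SE was 0.208 against an empirical 0.179.

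Fourth, the protocol wants safety assessed conservatively, and a larger SE makes non-inferiority harder to declare. That is correct. The protocol also says that adoption depends on being able to demonstrate safety, and avoidable noise works against that.

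Last, the constrained model leans somewhat more on the random-effects covariance. This is a fair point and the reason for requiring an unstructured one.

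**Conclusion.** The point holds as a loss of efficiency. Under randomisation the planned contrast is not expected to be more precise than the constrained or baseline-adjusted one, and it is less precise whenever the true slope on baseline is below 1. The formula assumes balanced units and equal variances in the two periods.

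The size is a range. The variance reduction is 25% at ρ = 0.5, 5% at ρ = 0.9 and about nil under random-walk drift. Length-of-stay power gains about 1 to 14 points over stable SDs of 0.03 to 0.15 and hospital-period SDs of 0 to 0.03.

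Three stronger readings should be resisted:

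- That the four-year gap makes the slope well below 1. The documents give neither the between-period correlation nor any hospital variance.
- That freeing β1 explains why power for length of stay may fall short of 91.5%, or that removing it restores that figure. Most of the shortfall comes from the difference-in-differences floor of about 70% and from any hospital-period variation. The power simulation left that variation out by drawing both periods from the same 2019 data. How the 91.5% was obtained, and whether it means power to show non-inferiority or to detect an increase, is a separate question.
- That the Cox models certainly contain a free baseline arm effect. Their fixed effects are unstated, and the link rests on the SAP's sentence about all outcomes.

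**What to change.** 1. Write out the fixed effects of every model, including the Cox models for length of stay and ICU transfer, and name the coefficient that each test uses.
2. If no outcomes by arm have been seen, remove the arm main effect, keep period and arm by period, and give (b0h, b1h) an unstructured covariance. Alternatively, model intervention-period outcomes with each unit's baseline value as a covariate. Carry the same choice into the Cox models and report difference in differences as a sensitivity analysis.
3. If outcomes by arm have been seen, keep difference in differences as primary and report the constrained model as a labelled sensitivity analysis.
4. Report the estimated between-period correlation of unit means, so that readers can judge the gain.

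No new data are needed, because the 2019 values are already part of the analysis. The cost is an SAP amendment that departs from a pre-specified model and must be dated and justified, plus slightly more reliance on the random-effects covariance.

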The INSPIRE-ASP Trial (INtelligent Stewardship Prompts to Improve Real-time Empiric Antibiotic Selection for Patients) for Abdominal (ABD) Infections Protocol

NCT:05423743

6/24/2020

Brief Overview

The **INSPIRE-ASP Trial (INtelligent Stewardship Prompts to Improve Real-time Empiric Antibiotic Selection for Patients) for Abdominal (ABD) Infections** is a cluster-randomized trial of 92 hospital randomized units (102 individual hospitals) to improve physicians' choice of antibiotics for patients hospitalized with ABD infections by reducing the unnecessary use of extended-spectrum antibiotics. This trial provides prescribers in half the hospitals with prescribing advice based on the probability that a patient is infected with antibiotic resistant bacteria. Provision of unnecessary extended-spectrum antibiotics carry risks, and the goal of this trial is to limit their use to situations in which the patient is likely to require them, while maintaining excellent patient outcomes.

We hypothesize that providing clinicians with individual patient risk estimates for antibiotic-resistant infections will reduce the overuse of empiric extended-spectrum antibiotics among patients hospitalized for ABD infections. To do this, we will use patient information in the electronic health record plus local hospital laboratory data on antibiotic resistance in ABD cultures to develop an automated smart tool that provides the likelihood that a patient needs extended-spectrum antibiotics. 102 hospitals were randomized into 92 hospital units, into either routine care (46 hospital units) or to the intervention arm (46 hospital units) receiving the INSPIRE Stewardship Bundle which includes CPOE smart prompts, clinician feedback reports, and activities to support CPOE adoption (e.g., education and modifications of CPOE workflows as needed). In half of these hospitals, physicians will be prompted to use standard-spectrum antibiotics when the risk of antibiotic-resistant infection is low. This 12-month intervention will evaluate approximately 99,000 patients with ABD infections.

Protocol Summary

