- Provide information on how to install the computerized physician order entry (CPOE) risk calculator into your local Meditech system
- Detail the toolkit that you will receive for intervention guidance
- Describe the feedback and audit reports

[figure not shown]
D. Study Design and Population

Title:	The INSPIRE-ASP Trial (INtelligent Stewardship Prompts to Improve Real-time Empiric Antibiotic Selection for Patients) for Abdominal (ABD) Infections.
Study Design:	Cluster-randomized trial
Participant:	102 Hospitals affiliated with HCA Healthcare randomized into 92 units. Hospitals with shared antibiotic stewardship teams (physicians or pharmacists) are randomized together as a single hospital unit. Inclusion criteria includes affiliation with HCA Healthcare and use of Meditech (for standardized build of CPOE prompts for the INSPIRE Stewardship Bundle arm). Any qualifying facility wishing to participate will be permitted to enroll even if in excess of calculated study sample size to accommodate HCA Healthcare facility or division-level antibiotic stewardship goals. Exclusion criteria include care of <100 ABD infection patients per year, and implementation or planned implementation of a new antibiotic stewardship intervention directly conflicting with the trial in the baseline or intervention period.
Population:	The analytic cohort will be patients with ABD infection. Inclusion criteria include adults ≥18 years old admitted to a general medical or surgical floor (non-ICU) of a participating HCA Healthcare hospital with a diagnosis of ABD infection. In addition, patients must receive a systemic antibiotic in the first 3 days of hospitalization (empiric period). Exclusion criteria will include age <18 years old and ICU admission on either hospital day 1 or 2. Hospitals that do not use Meditech are excluded from participation, as are those who use/will use Meditech Expanse or Patient Keeper for order entry.
Number of Sites:	92 HCA Healthcare hospital units (102 individual hospitals)
Study Duration:	5-month phase-in period (does not contribute to analysis) and 12-month intervention period
Subject Duration:	Eligible hospital admission
Schematic of Study Design:	

Figure 1: Two Study Arms of the INSPIRE-ASP Trial

Arm 1: Routine Care (N = 46 hospital units)

- Routine prescribing practice for ABD
- Pharmacy team prompts about bug-drug mismatch after cultures return

E. Study Procedures

E.1. Randomization

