The unit of analysis will be individual admissions. Individuals can contribute more than one admission. The analytic model will be a generalized linear mixed effects model for differences in differences, with random effects accounting for correlation within cluster, period-varying random effects to allow for differences within hospitals between baseline and follow-up, and admission-level random effects to account for correlation within person and hospital, if sufficient data exist. We plan to use a Poisson model for analysis of outcomes as follows:

$$\log(y_{ijph}) = \beta_0 + \beta_1 A_{ijph} + \beta_2 T_{ijph} + \beta_3 A_{ijph}T_{ijph} + b_{0h} + b_{1h}T_{ijph} + g_j + \log(ed_j)$$

where y_{ijph} is the ES-DOT for patient i for admission j in period p at hospital h , and $A_{ijph} = 1$ if hospital h is in the intervention arm and 0 if not, and $T_{ijph} = 1$ if p is the intervention period and 0 if baseline period. The random effects b_{0h} and b_{1h} allow for different baseline mean admission-level ES-DOT for each hospital and each hospital in the intervention period, respectively. Equivalently, they allow for correlation within hospital at different levels at baseline and at follow-up. The random effect g_j allows each patient to have a different mean ES-DOT. Finally, ed_j is the number of empiric days in the admission.

The assessment of trial success will be determined by the significance of the arm by period interaction term β_3 , which assesses whether the log relative rate of the outcome due to being in the intervention arm in the intervention period is different from 0. The exponentiated parameter estimate for β_3 is the estimated relative rate of ES-DOT per at-risk day due to the intervention, relative to the baseline period. For example, if β_3 had a negative value and a p-value <0.05 , we would conclude that the patient-specific CPOE smart prompts generated a benefit over routine care. Exponentiating the parameter value would provide an estimate of the relative reduction due to the intervention in the expected ES-DOT per at-risk day.

The primary trial analysis will use an as-randomized unadjusted model with two-tailed significance set at alpha = 0.05. Secondary outcomes will be assessed using an as-randomized unadjusted model and will include adjustment for multiple comparisons with two-tailed significance set at alpha = 0.025 for the two secondary outcomes.

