Abbreviations: **MRSA** - Methicillin Resistant *Staphylococcus aureus*; **VRE** – Vancomycin Resistant *Enterococci*; **ESBL** – Extended Spectrum Beta Lactamase producer; **CRE** – Carbapenem Resistant Enterobacteriaceae

Participating hospitals are randomized to:

- **Arm 1 – Routine Care**
- **Arm 2 – Real-Time Risk Estimation Smart Prompt**

Computerized physician order entry (CPOE) prompt that recommends standard-spectrum

antibiotics in patients admitted for ABD infections who are prescribed extended-spectrum antibiotics and calculated to have low risk (<10%) for an antibiotic resistant infection.

Trial Outcomes

Table 2: Primary and Secondary INSPIRE-ASP Abdominal Infections Trial Outcomes

Outcome	Metric
Primary Trial Outcome	
Total Empiric Extended-Spectrum Antibiotic Days of Therapy (ES-DOT)	The number of different extended-spectrum antibiotics received by the patient each empiric day, summed across the first 3 days of hospitalization. ¹
Secondary Trial Outcomes	
Vancomycin Days of Therapy per Empiric Day	The number of days Vancomycin was received by the patient on the first 3 days of hospitalization. ¹
Total Empiric Antipseudomonal Antibiotic Days of Therapy	The number of different antipseudomonal antibiotics received by the patient each empiric day, summed across the first 3 days of hospitalization. ¹

¹E.g., if a patient is admitted for 2 days, ES-DOT will be calculated across those 2 days; however if a patient is admitted for 4 days, only the first 3 days will be evaluated.

Safety outcomes planned for the primary manuscript are shown in Table 3. Length of stay and days to ICU transfer are evaluated within 14 days of admission since empiric antibiotic selection within the first 3 hospital days is not expected to be the main driver of either outcome beyond this time; evaluation of baseline data also shows that 93% of abdominal patients have length-of-stay equal to or less than 14 days.

Table 3: Other Pre-Specified Outcomes – Trial Safety Outcomes

Safety Trial Outcomes (other pre-specified outcomes)	
ICU Transfer [Safety Outcome]	Days to ICU transfer, between hospital days ≥ 3 and ≤ 14 .
Length-of-stay [Safety Outcome]	Days from hospital admission until discharge or hospital day 14, whichever comes first, where admission day is hospital day 1.

Data Collection Details

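### The trial randomises 92 units built from 102 hospitals, but the SAP indexes its random effects by hospital; if that means the individual hospital, and changes correlate within units, the arm-by-period standard error is too small

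*SAP*

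**What the plan says.** The protocol's Brief Overview states that "102 hospitals were randomized into 92 hospital units", 46 per arm. Section D gives the reason: "Hospitals with shared antibiotic stewardship teams (physicians or pharmacists) are randomized together as a single hospital unit". Its Number of Sites row counts units and individual hospitals separately. In section H.3 the model description refers to "random effects accounting for correlation within cluster", but the equation that follows carries the subscript h, defined only as hospital.

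The SAP does not mention the randomised unit. Its Background says "Participating hospitals are randomized to" the two arms. Under Primary Statistical Analysis the arm indicator equals 1 "if hospital h is in the intervention arm and 0 if not", the random terms b_0h and b_1h are defined for each hospital, and the model is described as having "random effects to account for correlation within hospital between period, within hospital within period between patient, and within patient between admission". Trial success rests on the significance of β_3, the arm-by-period term, at two-sided 0.05; each of the two secondary outcomes is tested at two-sided 0.025. The safety section lists random effects for period, hospital and admission. The protocol's safety paragraph in H.3 lists only hospital and admission. Neither document gives the number or sizes of multi-hospital units, and neither plans a unit-level effect, a robust variance or a sensitivity analysis at unit level.

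**The concern.** The standard error of a treatment effect in a cluster-randomised trial should reflect the level that was allocated. Read literally, the SAP model treats two hospitals that were allocated together as two independent pieces of evidence.

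A baseline level shared within a unit largely cancels in a difference-in-differences. What does not cancel is shared change between 2019 and 2023. Some shared change is plausible here, because a multi-hospital unit is defined by its common stewardship team, and the protocol makes stewardship leaders the study champions who run local implementation and feed results back to prescribers. The documents give no value for this correlation. If it is positive and h is the individual hospital, the test of β_3 rejects more often than its stated level and the confidence intervals are too narrow.

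**Working it through.** **Figures in the plan.** The documents give no type I error under clustering to reproduce; the reference is the stated alpha, which the formula below returns at correlation 0. The stated primary power of at least 99.9% comes from a bootstrap of 2019 records and cannot be rebuilt from the published inputs. It is not at issue here. In that bootstrap "individuals were selected with replacement from within each hospital, once to represent baseline data and separately to represent" the intervention period, so it carries no information on how hospital changes vary, and the multiples below do not apply to it.

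**Inputs from the documents.** 102 hospitals; 92 units; two-sided alpha 0.05 (primary) and 0.025 (each secondary outcome).

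**Assumed inputs, none given.**
- m_k, the number of hospitals in unit k.
- ρ, the within-unit correlation of the hospital-by-period effects.
- s, the share of the variance of a hospital's observed change that is hospital-by-period variance; the rest is patient-level sampling error.
- Equal weight for each hospital.

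**Unit sizes.** Every unit has at least one hospital, which leaves 102 − 92 = 10 extra. Under equal weights, Σ m_k(m_k − 1) is smallest when these fall in ten different units: ten pairs and 82 singles give 10 × 2 × 1 = 20. Five triples and 87 singles give 5 × 3 × 2 = 30.

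**Formulas.**
- Ratio of true to modelled variance of β_3: VR = 1 + s·ρ·Σ m_k(m_k − 1)/102.
- Standard error multiple: √VR.
- Actual two-sided error: 2·(1 − Φ(1.960/√VR)) for the primary test and 2·(1 − Φ(2.241/√VR)) for a secondary test.

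**Example.** Ten pairs, s = 1, ρ = 1: VR = 1 + 20/102 = 1.196; √VR = 1.094; 1.960/1.094 = 1.792; two-sided error 7.3%.

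**Results for ten pairs.**

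| s | ρ | SE multiple | Primary (nominal 5%) | Secondary (nominal 2.5%) |
|---|---|---|---|---|
| any | 0 | 1.000 | 5.0% | 2.5% |
| 0.25 | 0.25 | 1.006 | 5.1% | 2.6% |
| 0.25 | 0.5 | 1.012 | 5.3% | 2.7% |
| 0.5 | 0.25 | 1.012 | 5.3% | 2.7% |
| 0.5 | 0.5 | 1.024 | 5.6% | 2.9% |
| 1 | 0.25 | 1.024 | 5.6% | 2.9% |
| 1 | 0.5 | 1.048 | 6.1% | 3.2% |
| 1 | 1 | 1.094 | 7.3% | 4.0% |

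Fewer, larger units give more. Five triples at ρ = 1 give a multiple of 1.138 and 8.5% when s = 1, or 1.071 and 6.7% when s = 0.5.

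**Simulation check.** The setting was 46 against 46 units, ten pairs split five per arm, no true effect, and 320,000 trials per setting. A t-test on hospital-level changes rejected in 5.0%, 5.6%, 6.2% and 7.3% of trials at ρ = 0, 0.25, 0.5 and 1 with s = 1, and in 5.1%, 5.3%, 5.6% and 6.1% with s = 0.5. A t-test on unit-level changes stayed between 4.9% and 5.1% in every setting. This checks the variance argument; it does not fit the planned Poisson mixed model.

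**Safety models.** The variance ratio presumes a model that already contains a hospital-by-period term and omits only the correlation within units. The primary model has that term (b_1h). The SAP's list for the safety models does not make clear whether period and hospital enter separately or as hospital-by-period, and the protocol lists no period term. No safety error rate is therefore computed.

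**The case against.** The best reply is that hospital is shorthand. The protocol, having defined the unit, still speaks loosely of randomising hospitals, including in its consent section and its power description. It also calls the design a cluster-randomised trial of 92 units and models correlation within cluster, which most naturally means the unit. The SAP's wording is then weak evidence that the analysts will code 102 hospitals. This stands: what the documents show is an undefined index. A reader might infer that the sponsor intends to ignore the randomised unit; the documents do not support that.

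A second reply is that the effect is small. This stands in part. At moderate correlation with a half or quarter share, the error is 5.1% to 5.6%. The larger figures need hospitals with separate patients and prescribers to change identically, and nothing in the documents supports such a value. A reader might infer that material error inflation is established; it is not.

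Third, ten pairs is a minimum only under equal weights. When sampling error matters, the mixed model weights hospitals partly by volume. The inflation would be less if team-sharing hospitals are small and more if they are large. Volumes are not given.

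Finally, a reader might carry these error rates over to the one-sided non-inferiority tests. The random-effect structure described for those models is too unclear to support that.

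**Conclusion.** The mismatch between the allocated level and the level named in the SAP model is real, and h needs a definition on either reading. An understated standard error for β_3 follows only if h is coded as the individual hospital and changes are positively correlated within units. Within the ranges assumed for ten equally weighted pairs, the primary error lies between 5% (no correlation) and 7.3% (correlation 1 with hospital-by-period variance dominant), with 5.1% to 6.1% covering correlations of 0.25 to 0.5. These are conditional illustrations. The point is worth acting on because β_3 alone decides the trial and the correction is nearly free. No claim is made about the stated power or about the error rates of the safety tests.

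**What to change.** State in the SAP that the cluster index is the randomised unit, and put b_0 and b_1 on the 92 units in the primary and secondary Poisson models. Hospital effects nested within unit are optional where they can be estimated. In the safety frailty models, replace the hospital random effect with the randomised unit in the same way. Reporting the distribution of unit sizes would let readers judge how much the choice matters.

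The cost is one sentence in the SAP, a unit identifier in the analysis file, and possibly slightly wider intervals for the primary and secondary outcomes.

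Whether the safety models should also have a unit-by-period effect is a separate question and not part of this change, because it may add a variance component. As an illustration, suppose the true hazard ratio is 1. The stated 91.5% length-of-stay power against the 0.98 margin then implies a standard error of 0.0202/(1.645 + 1.372) = 0.0067. An assumed between-unit SD of change of 0.02 to 0.03 in the log hazard ratio adds SD² × 2/46 to the variance. That raises the standard error by 18% to 37% and lowers power to about 82% to 71%. The sponsor should decide that point on its own merits.
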